**Table 2. Discontinuation Criteria for Subjects with Underlying Bundle Branch Block**

Baseline QTcF with Bundle Branch Block	Discontinuation QTcF Threshold with Bundle Branch Block
<450 msec	>500 msec
450 to 500 msec	≥530 msec

#### **4.4.2.6. Pregnancy**

For all female subjects of childbearing potential, a pregnancy test will be performed at the times indicated in the SOA ([Appendix 1](#)). Subjects testing positive for pregnancy at Screening or prior to dosing will be ineligible for study participation. Subjects testing positive for pregnancy during the study will be withdrawn from the study. Refer to [Section 7.3.3](#) for follow-up procedures for subjects who become pregnant during the study.

#### **4.4.3. Lost to Follow-up**

A subject will be considered lost to follow-up if he/she repeatedly fails to return for scheduled visits and is unable to be contacted by the study site.

The following actions must be taken if a subject fails to return to the clinic for a required study visit:

- The site must attempt to contact the subject and reschedule the missed visit as soon as possible, counsel the subject on the importance of maintaining the assigned visit schedule and ascertain whether or not the subject wishes to and/or should continue in the study.
- In cases in which the subject is deemed lost to follow-up, the Investigator or designee must make every effort to regain contact with the subject (where possible, 3 telephone calls and, if necessary, a certified letter to the subject's last known mailing address or local equivalent methods). These contact attempts should be documented in the subject's medical record. This level of diligence is necessary to obtain (at minimum) vital status (whether the subject is alive), and thus avoid being lost to follow-up for efficacy and safety assessment.
- Should the subject continue to be unreachable, he/she will be considered lost to follow-up. In this case, every attempt should be made to search public health records for the subject's vital status and document findings in the eCRF.

#### **4.4.4. Subject Replacement**

Subjects who are withdrawn from the study may not re-enter the study but may be replaced at the Sponsor's discretion.

### **4.5. Study Termination**

#### **4.5.1. Early Termination of the Study**

The Sponsor reserves the right to close a study site or terminate the study at any time for any reason at the sole discretion of the Sponsor. If the Steering Committee, Data Monitoring Committee (DMC), Sponsor, or regulatory officials discover conditions arising during the study that indicate that the study should be halted or terminated, this action may be taken after appropriate consultation between the Steering Committee, Sponsor, and the DMC. Full details on the roles of the Steering committee and DMC will be provided in each committee's respective charter. Conditions that may warrant termination of the study include, but are not limited to, the following:

- The discovery of an unexpected, serious, or unacceptable risk to the subjects enrolled in the study;
- AEs unknown to date (i.e., not previously reported in any similar investigational study drug trial with respect to their nature, severity, and/or duration);
- Increased frequency and/or severity and/or duration of known, anticipated, or previously reported AEs (this may also apply to AEs defined at check-in as Baseline signs and symptoms);
- Medical or ethical reasons affecting the continued performance of the study;
- Difficulties in the recruitment of subjects;
- A decision on the part of the Sponsor to suspend or discontinue testing, evaluation, or development of the study drug.

Study sites will be closed upon study completion. A study site is considered closed when all required documents and study supplies have been collected and a study site closure visit has been performed.

#### **4.5.2. Early Termination of a Study Center**

Conduct of the study at a particular center may be terminated by the Sponsor or Investigator for the following reasons, but are not limited to:

- Failure of the Investigator to comply with the protocol, the requirements of the Institutional Review Board (IRB)/Ethics Committee (EC) or local regulatory and/or health authorities' regulations, the Sponsor's procedures, or ICH/GCP guidelines;
- Inadequate recruitment of participants by the Investigator;
- Submission of knowingly false information from the research facility to the Sponsor, Sponsor-designated contract research organization (CRO) or vendors, study monitor, the FDA, and/or other applicable regulatory authorities.

The Investigator may initiate study site closure at any time, provided there is reasonable cause and sufficient notice is given in advance of the intended termination.

If a study center or Investigator is terminated, the Sponsor will make all efforts possible to have another investigative site assume responsibility for continuing trial activities.

Study termination and follow-up will be performed in compliance with the conditions set forth in the following sections of the Code of Federal Regulations (CFR): 21 CFR 312.50 and 21 CFR 312.56, and other local regulatory authorities.

## **5. STUDY TREATMENTS**

For Cohort A after randomization, subjects will be administered namilumab 150 mg or placebo via SC injection on Day 1 (Baseline) and then at Weeks 2, 6, 10, 14, 18, 22, 26, and 30. In addition, these subjects will begin tapering their prednisone or equivalent per the guidelines in [Appendix 8](#).

Subjects in Cohort B will be administered namilumab 150 mg via SC injection on Day 1 (Baseline) and then at Weeks 2, 6, 10, 14, 18, 22, 26, and 30, in addition to their prior low-dose prednisone or equivalent.

The study drug eCRF will be completed each time study drug is dispensed.

## 5.1. Treatments Administered

The identity, potency/strength, and appearance of the study drug used are presented in [Table 3](#). It should be noted that the vials for both placebo and study drug will be masked to maintain the blind in Cohort A.

**Table 3. Description of Study Treatments**

Study Treatment Name	Namilumab	Placebo
Dosage Formulation:	Solution for injection	Solution for injection
Unit Dose	150 mg	Each vial contains 1.2 mL
Strength(s)/Dosage Level(s):	Each vial contains 1.2 mL	
Route of Administration:	SC injection, which may be administered in the thigh, abdomen, or upper arm	SC injection, which may be administered in the thigh, abdomen, or upper arm
Dosing Instructions:	1 mL administered	1 mL administered
Packaging and Labeling:	Study treatment will be provided in a sterile, single-use glass vial containing 1.2 mL of solution. Each vial will be labeled as required per country requirement.	Study treatment will be provided in a vial containing 1.2 mL of solution. Each vial will be labeled as required per country requirement.

## 5.2. Preparation, Storage, Handling, and Accountability

Study drug will be provided in sterile, single-use, masked glass vials. Each vial contains 1.2 mL drug product or placebo solution to ensure a withdrawal volume of 1 mL for SC injection.

The Investigator or designee must confirm appropriate temperature conditions have been maintained during transit for all study drug received and any discrepancies are reported and resolved before use of the study drug.

Namilumab and placebo must be stored at 2°C to 8°C (36°F to 46°F).

All study drugs must be stored in a secure, environmentally controlled, and monitored (manual or automated) area in accordance with the labeled storage conditions with access limited to the Investigator and authorized site staff.

Only subjects enrolled in the study may receive study drug and only authorized site staff may supply or administer study drug.

### **5.2.1.     Return of Study Drug**

Vials of used, partially used, and unused study drug products should be retained until the clinical research associate (CRA) has been able to complete drug accountability and reconciliation. If retention of used vials is not allowed per site standard operating procedure(s) then approval for immediate destruction must be approved by the Sponsor.

Upon completion or termination of the study, all unused and/or partially used study drug must be returned to the Sponsor or designee, if not authorized by the Sponsor to be destroyed at the site.

All study drug returned to the Sponsor or designee, or other authorized party must be accompanied by the appropriate documentation and be clearly identified by protocol number and study site number on the outermost shipping container. Returned supplies should be in the original vials (e.g., vials that have clinical labels attached). Empty vials should not be returned to the Sponsor or designee. It is the Investigator's responsibility to arrange for disposal and destruction of all empty vials, provided that procedures for proper disposal have been established according to applicable federal, state, local, and institutional guidelines and procedures, and provided that appropriate records of disposal are kept. The return of unused study drug should be arranged by the assigned CRA.

### **5.2.2.     Destruction of Study Drug**

If study drug is to be destroyed at the site, it is the Investigator's responsibility to ensure that arrangements have been made for the disposal, written authorization has been granted by the Sponsor, procedures for proper disposal have been established according to applicable regulations and guidelines and institutional procedures, and appropriate records of the disposal have been documented and provided to the Sponsor or designee. Unused study drug can only be destroyed after being inspected, reconciled by the responsible CRA and Sponsor approval has been obtained in writing.

Further guidance and information for the final disposition of unused study drug are provided in the Pharmacy Manual.

## **5.3.     Treatment Assignment and Administration**

Once a subject is confirmed as eligible for study participation, the subject will be randomized (if in Cohort A) using the Interactive Response Technology (IRT) system. The IRT system will also be used for subjects in Cohort B in order to assign the appropriate vial/kit number at each clinic visit. Study drug will be dispensed at the study visits summarized in the SOA ([Appendix 1](#)). Study drug will be administered via SC injection, which may be administered in the thigh, abdomen, or upper arm.

Returned study drug should not be re-dispensed to the subjects.

### **5.3.1.     Dose Modification**

Dose reductions will not be allowed. If a dose reduction is needed, the subject should be discontinued from study drug and all EOT assessments completed. See [Section 4.4.2.2](#) for missed doses.

## **5.4. Blinding**

Namilumab and placebo are not visually identical. Study drug will be provided in a blinded fashion and packaged and labeled to protect the blind. Sites will be provided with masked syringes to administer the study drug.

Subjects in Cohort A will be randomized 1:1 to namilumab or placebo using the IRT. At the time of randomization, subjects will be assigned a randomization number by the IRT. Subjects in Cohort B will receive unblinded study drug.

The Investigator will have the ability to unblind a subject using the IRT system. The study blind may be broken by the Investigator using the IRT if, in the opinion of the Investigator, it is in the subject's best interest to know the study drug assignment. The Sponsor must be notified before the blind is broken unless identification of the study drug is required for a medical emergency in which the knowledge of the specific blinded study drug will affect the immediate management of the subject's condition.

## **5.5. Treatment Compliance**

### **5.5.1. Study Drug Compliance**

The Investigator must maintain accurate records of study drug receipt, dispensing information and disposition. Sponsor will provide forms to facilitate inventory control, if the staff at the investigational site does not have an established system that meets these requirements.

Treatment compliance will be calculated based on number of used vials returned for each subject.

### **5.5.2. Corticosteroid Use and Taper Compliance**

Corticosteroids (OCS) will be self-administered by the subjects during the study. At each study visit, Investigators must review and document a subject's compliance with OCS use and taper during the corticosteroid tapering period and throughout the study until the subject completes their EOT/ET Visit. In order to verify corticosteroid dose on a daily basis, subjects will be required to complete an eDiary to document their steroid intake.

## **6. CONCOMITANT THERAPIES AND OTHER RESTRICTIONS**

### **6.1. Concomitant Therapy**

Any medication or vaccine (including over-the-counter or prescription medicines, vitamins, and/or herbal supplements) that the subject is receiving at the time of enrollment or receives during the study must be recorded along with:

- reason for use;
- dates of administration, including start and end dates;
- dosage information including dose and frequency.

The Medical Monitor should be contacted if there are any questions regarding concomitant or prior therapy.

## 6.2. Prohibited Medications/Therapies

The following medications are prohibited during the study:

- Recombinant GM-CSF (e.g., sargramostim, molgramostim);
- Recombinant granulocyte colony-stimulating factor (e.g., filgrastim, lenograstim, pegfilgrastim, lipegfilgrastim);
- Kinase inhibitors, including JAK inhibitors (e.g., baricitinib, tofacitinib, ruxolitinib, upadacitinib) and Bruton's tyrosine kinase inhibitors (e.g., ibrutinib, acalabrutinib, zanubrutinib);
- Biologic agents targeting one or more specific cytokines or cytokine receptors, including but not limited to mAbs inhibiting TNF (e.g., adalimumab, etanercept, infliximab, golimumab, certolizumab), interleukin (IL)-1 (e.g., anakinra, canakinumab), IL-6 (e.g., tocilizumab, sarilumab, siltuximab), IL-17 (e.g., secukinumab, ixekizumab, brodalumab), IL-12/23 (e.g., ustekinumab), selective inhibitors of IL-23p19 (e.g., guselkumab, tildrakizumab, risankizumab);
- Biologic agents targeting one or more specific molecules expressed on immune cells, including but not limited to mAbs against CD20 (e.g., rituximab) and CD3 (e.g., otelixirizumab, teplizumab, visilizumab);
- Agents targeting the complement pathway (e.g., eculizumab, berinert, cinryze);
- IV (or SC) Ig;
- Any other investigational agent not approved by the FDA;
- Vaccines in general are not permitted with the exception of COVID-19 booster shots and routine Flu shots.

The Medical Monitor should be contacted if there are any questions regarding whether a medication is prohibited. If a prohibited medication must be used due to clinical decline of a subject, the medication will be counted as a rescue medication.

New use of ISTs, including methotrexate, azathioprine, or mycophenolate mofetil, is subject to the rescue requirements discussed in [Section 6.4](#).

## 6.3. Contraception

Females of childbearing potential who participate in this study must use highly effective contraceptive methods from at least 28 days prior to randomization, throughout the study, and for at least 8 weeks (56 days) post last dose of study drug. For this study, females are of childbearing potential following menarche and until becoming postmenopausal unless permanently sterile. Permanent sterilization methods include total hysterectomy, bilateral oophorectomy, bilateral salpingectomy, bilateral tubal ligation, or bilateral hysteroscopic sterilization at least 3 months prior to Screening. A postmenopausal state is defined as no menses for 12 months without an alternative medical cause. A high serum FSH level in the postmenopausal range

(FSH  $\geq 30$  mIU/mL) may be used to confirm a post-menopausal state in women not using hormonal contraception or hormonal replacement therapy. Any use of hormonal contraception must be documented in the subject's chart as a concomitant medication.

For this study, the following methods of contraception are considered to be acceptable effective contraceptive measures (based on annual failure rate of  $<1\%$  when used consistently and correctly):

- Combined (estrogen and progestogen containing) hormonal contraception associated with inhibition of ovulation:
  - Oral;
  - Intravaginal;
  - Transdermal.
- Progestogen-only hormonal contraception associated with inhibition of ovulation:
  - Oral;
  - Injectable;
  - Implantable.
- Intrauterine device;
- Intrauterine hormone-releasing system;
- Vasectomized male partner provided that partner is the sole sexual partner of the female study subject.
- Sexual abstinence: Note: sexual abstinence is considered a highly effective method only if defined as a refraining from heterosexual intercourse during the entire study period of risk associated with the study treatments; for this study that includes 28 days prior to randomization/enrollment, throughout the study and, for 8 weeks (56 days) following the last dose of study drug. The reliability of sexual abstinence needs to be evaluated in relation to the duration of the clinical trial and the preferred and usual lifestyle of the subject. The Investigator must confirm at every clinic visit that subject is still practicing sexual abstinence and document the discussion in the subject's source documents.

Male subjects must agree to, and attest that, female partners of childbearing potential are using one of the allowed highly effective methods of contraception as described above for at least 28 days prior to randomization/enrollment, throughout the study, and for 8 weeks (56 days) following the last dose of study drug.

Urine pregnancy testing for all females of childbearing potential will be performed as specified in the SOA ([Appendix 1](#)). Any positive urine test result must be confirmed based on a serum pregnancy test. The Investigator may perform additional pregnancy tests at their discretion or as required by local regulations.

## 6.4. Rescue Therapy

The clinical status of a subject in either Cohort may deteriorate. The Investigator should instruct subjects to contact study staff immediately if they feel their symptoms or signs of sarcoidosis, particularly of their cardiac disease, are worsening.

The Investigator may assess that the clinical deterioration is due to progression of CS and may wish to provide rescue therapy. In this circumstance, increased OCS dosing at the lowest effective increment with the shortest duration is the preferred option so that integrity of the study may be preserved. Alternatively, the change in regimen may be increased dosing of a current IST or the addition of a new one.

In this protocol rescue therapy is defined as any of the following:

- (Cohort A) Failure of the OCS taper, i.e., the subject requires an increase in OCS dose during the protocol-specified taper ([Appendix 8](#));
- (Cohort A) Protocol-specified dose levels cannot be reached by the pre-specified timepoints ([Appendix 8](#));
- (Cohort A) Increase in OCS dose above 10 mg/day prednisone, or equivalent, after the taper is complete;
- (Cohort B) Increase in OCS dose above 10 mg/day prednisone, or equivalent, at any time;
- (Either Cohort) Start of a new IST or change in dose or frequency of a current IST;
- (Either Cohort) Use of a prohibited medication to treat sarcoidosis-related signs or symptoms.

The following do not constitute rescue therapy:

- Use of OCS for up to 14 days or less for treatment of an event not related to sarcoidosis, e.g., an acute allergic reaction, acute contact dermatitis;
- Use of inhaled OCS or bronchodilators, e.g., long-acting beta agonists or long-acting muscarinic agonists.

Prior to initiating rescue therapy in a subject who is not hospitalized, an unscheduled visit should be performed; see [Sections 3.1.4](#) and [3.1.4.1](#) for details.

If it would not adversely affect a subject's safety or wellbeing, PET/CT and TTE should be performed before initiation of rescue therapy.

Cohort A subjects should resume the protocol-specified steroid taper ([Appendix 8](#)) at the earliest opportunity based on the Investigator's clinical judgement.

The Medical Monitor must be contacted if rescue therapy is initiated, and the reason(s) should be captured in source records and in the CRF.

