MGC(s)	multinucleated giant cell(s)
mGTI	modified glucocorticoid toxicity index
mITT	modified Intent-to-Treat
mRNA	messenger ribonucleic acid
NT-proBNP	N-terminal (NT)-pro hormone brain natriuretic peptide
NYHA	New York Heart Association
OCS	oral corticosteroid(s)
OLE	open-label extension
PAP	pulmonary alveolar proteinosis
PE	physical examination
PET	positron emission tomography
PK	Pharmacokinetic(s)
PP	Per-Protocol
PPK	population pharmacokinetics
PRO(s)	patient-reported outcome(s)
PTCA	percutaneous transluminal coronary angioplasty
PV	pharmacovigilance
Q4W	every 4 weeks

QTcF	Fridericia corrected QT interval
RA	rheumatoid arthritis
RBC(s)	red blood cell(s)
RT-PCR	real time-polymerase chain reaction
SAA	serum amyloid A
SAE(s)	serious adverse event(s)
SAP	statistical analysis plan
SC	subcutaneous(ly)
SD	standard deviation
SGA	Subject Global Assessment
SOA	Schedule of Assessments
SOC	system organ class
SP	Safety Population
SP-D	serum surfactant protein D
TARC	thymus and activation-regulated chemokine
TB	tuberculosis
TC	total cholesterol
TEAE(s)	treatment-emergent adverse event(s)
TG(s)	triglyceride(s)
TNF	tumor necrosis factor
TTCW	time-to-clinical worsening
TTE	transthoracic echocardiography
ULN	upper limit of normal
VEGF	vascular endothelial growth factor
WBC(s)	white blood cell(s)
WCBP	woman of childbearing potential

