#### **Secondary Endpoints:**

- Other safety endpoints including:
  - Incidence and magnitude of treatment-emergent laboratory abnormalities;
  - Change from baseline in vital signs;
  - Change from baseline in ECG parameters.

- Mean change from baseline in PET maximum standardized update value (SUVmax), SUVmean, and total glycosylation;
- Cumulative arrhythmia burden and hospitalization for cardiac events;
- Mean change from baseline in left ventricular ejection fraction (LVEF) and global longitudinal strain (GLS) on transthoracic echocardiogram (TTE);
- Cumulative oral steroid use, modified glucocorticoid toxicity index (mGTI), and mean change from Baseline in glycosylated hemoglobin (HbA1C);
- Proportion of subjects requiring rescue therapy (either cohort) and proportion of subjects successfully achieving steroid taper without requiring rescue therapy (Cohort A);
- Mean change from baseline in KSQ (General and sub-domains), Fatigue Assessment Scale (FAS), and Subject Global Assessment (SGA);
- Assessments of PPK and E-R relationships for safety and efficacy if data permit.

**Note:** For endpoints defined as mean change from baseline, the primary assessment will be at Week 34.

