## 4.2. Exclusion Criteria

**An individual will not be eligible for participation in this study if any of the following exclusion criteria are met:**

1. Hospitalized for any respiratory or cardiac illness  $\leq 30$  days prior to Screening.
2. Known pulmonary hypertension requiring therapy.
3. Systemic (oral or parenteral) antibiotic or pulse OCS treatment for any indication within 42 days prior to randomization.
4. Autoimmune disease other than sarcoidosis likely to require treatment during the subject's participation in this study.
5. Symptoms and/or signs of extracardiac sarcoidosis that are likely to warrant treatment in addition to that required for the subject's cardiac disease.
6. Estimated glomerular filtration rate (eGFR)  $\leq 30 \text{ mL/min/1.73 m}^2$  (Modification of Diet in Renal Disease [MDRD] equation) or requiring renal replacement therapy.
7. Alanine aminotransferase (ALT), aspartate aminotransferase (AST), or alkaline phosphatase (ALP)  $> 2 \times$  upper limit of normal (ULN).
8. Platelet count  $< 100,000 \text{ per mm}^3$ .
9. Hemoglobin  $\leq 9.5 \text{ g/dL}$ .
10. Absolute neutrophil count  $< 1,000 \text{ per mm}^3$ .
11. Serum albumin-corrected calcium  $> 3.5 \text{ mmol/L (14 mg/dL)}$ .
12. Positive anti-GM-CSF autoantibody, or history of pulmonary alveolar proteinosis (PAP).
13. Use of any biologic immunomodulator (approved or investigational) within the 6 months prior to Screening. Allergens for hypersensitivity desensitization or vaccines are not excluded per this criterion. Treatment with immunoglobulin within 6 months prior to Screening. Treatment with any investigational immunomodulator (e.g., Neuropilin 2 [NRP2] modulator) within 6 months prior to Screening.
14. Treatment with any Janus kinase (JAK) inhibitor within 3 months prior to Screening.
15. Participation in another interventional clinical trial within 6 months prior to Screening and throughout the duration of participation in this study.

16. History of left ventricular ejection fraction (LVEF)  $\leq 30\%$  or NYHA class III or IV heart failure.
17. Fridericia corrected QT interval (QTcF)  $> 480$  msec on the 12-lead ECG at Screening; if QTcF exceeds 480 msec, the ECG should be repeated 2 more times and the average of the 3 QTcF measures should be used to determine eligibility.  
Note: If a subject has a pre-existing bundle branch block (BBB), the QTcF exclusion cutoff will be  $> 500$  msec.

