- j. Only central imaging interpretation will be accepted for eligibility determination. Scans conducted as part of the usual clinical management of the subject within 2 weeks prior to informed consent may be considered/assessed for use in place of the Screening PET/CT scan if the scans can be uploaded to central imaging vendor for central read and the OCS dose has not changed in the 4 weeks prior to the scan. Refer to [Section 7.1.2.1](#) for details
- k. Document whether the patient has completed taper by the specified timepoints described in [Appendix 8](#) or whether a dose increase/maintenance was needed. See [Section 6.4](#) for more details regarding rescue therapy. Patients should record OCS dose daily on provided eDiary.
- l. Collect information on concomitant medications and concurrent procedures from the time of informed consent through the EOS Visit, including prescription medications, over-the-counter medications, and herbal supplements/vitamins. All medications and procedures prior to randomization should be listed in the subject's medical history.
- m. All serious adverse events will be monitored and collected from the time of informed consent through the 8 weeks (56 day) post last dose of study drug FU. All adverse events will be monitored and collected from the time of randomization through the 8 weeks (56 day) post last dose of study drug FU. Treatment-emergent adverse events will be those that start or change in severity after the first dose of study drug.
- n. If necessary, follicle-stimulating hormone will be measured at Screening to confirm postmenopausal status.
- o. The ADA samples will be collected at Baseline (prior to the first dose) of Day 1 (Week 0), at Week 14, and at EOT. For subjects who terminate the study early, one ADA sample will be collected before discharging, when possible. Actual sampling time will be recorded.
- p. The PK samples will be collected prior to study drug administration at the appropriate timepoints and actual sampling time will be recorded.
- q. Investigators in the state of New York will remain blinded to the anti-GMCSF auto-antibody assay results until the end of the trial due to regulations within the state of New York.

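### The rescue list and the steroid endpoint name only oral corticosteroid, so intravenous or intramuscular steroid given for worsening sarcoidosis can go unscored

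*Combined protocol and SAP*

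**What the plan says.** Section 6.4 introduces its list with "In this protocol rescue therapy is defined as any of the following". For Cohort A the first item is that "the subject requires an increase in OCS dose during the protocol-specified taper". The other steroid items are Appendix 8 levels not reached on time, OCS above 10 mg/day after the taper (Cohort A), and OCS above 10 mg/day at any time (Cohort B). Two items apply to both cohorts: a new or changed IST, and a prohibited medication used for sarcoidosis. The List of Abbreviations expands OCS as oral corticosteroid.

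Section 6.2 names no corticosteroid by any route among the prohibited drugs. On ISTs it says "New use of ISTs, including methotrexate, azathioprine, or mycophenolate mofetil, is subject to the rescue requirements".

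Among the secondary endpoints in Section 2.2, the steroid line opens "Cumulative oral steroid use, modified glucocorticoid toxicity index (mGTI". The rescue endpoints are the proportion needing rescue (either cohort) and the proportion completing the taper without it (Cohort A). On recording, Appendix 1 footnote k says "Patients should record OCS dose daily on provided eDiary".

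Section 6.4 also anticipates rescue of inpatients, because it limits one requirement to outpatients: "Prior to initiating rescue therapy in a subject who is not hospitalized, an unscheduled visit should be performed".

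**The concern.** A subject may be treated for worsening cardiac sarcoidosis with a short parenteral steroid course and then continue the scheduled oral dose. On the literal text that treated deterioration is not a rescue. In Cohort A the subject could be reported as a taper success, and in Cohort B as not rescued. The parenteral dose would not enter the steroid endpoint in either cohort. If the episode involved an admission, the same subject could appear under hospitalization for cardiac events and under taper success.

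The definition also controls data collection. The Rescue Visit (Section 3.1.4.1), the PET/CT and echocardiogram before rescue where safe, and the contact with the Medical Monitor (Section 6.4) all depend on someone recognising the treatment as rescue. If nobody does, assessments meant to precede rescue may not be obtained, and later reclassification cannot recover them.

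**Working it through.** There is no planned figure to reproduce: Section 8.1 gives no power basis for the sample size, and no rescue rate is assumed. The check sets parenteral corticosteroid against each rule.

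**1. The six triggers in Section 6.4**

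- OCS increase during the taper (A): oral only.
- Appendix 8 level not reached (A): that appendix is the oral taper.
- OCS above 10 mg/day after the taper (A): oral only.
- OCS above 10 mg/day at any time (B): oral only.
- New or changed IST: Section 1 introduces ISTs as steroid-sparing drugs, Section 1.2 lists OCS and ISTs as separate things, and the examples in Section 6.2 include no steroid.
- Prohibited medication: no corticosteroid is on the Section 6.2 list.

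None of the six names non-oral steroid. The allowance for an equivalent of prednisone converts potency through Appendix 4 and does not add a route. The list of what is not rescue covers short oral courses for unrelated events and inhaled steroid. It does not mention intravenous or intramuscular steroid.

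**2. Recording**

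The eDiary covers OCS. Section 6.1 and Appendix 1 footnote l capture all medications, and Section 6.1 lists reason, dates, dose and frequency. A parenteral course would therefore be in the database, but no rule carries it into either endpoint. Section 6.1 does not list route among the items recorded.

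**3. Effect on a proportion**

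Cohort A has 10 subjects per arm and Cohort B has 10. One reclassified subject is 1/10 = 10 percentage points. With exact (Clopper-Pearson) 95% intervals, for example:

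- 2/10 = 20% (2.5% to 55.6%)
- 3/10 = 30% (6.7% to 65.2%)

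The proportion completing the taper without rescue can move by the same amount in the opposite direction.

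**4. Scale of the oral total**

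This is the lowest Appendix 8 schedule, assuming a linear decrease over Weeks 11-22 (mean (25 + 10)/2 = 17.5 mg/day) and 10 mg/day afterwards:

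- Weeks 1-4: 25 × 28 = 700 mg
- Weeks 5-10: 25 × 42 = 1,050 mg
- Weeks 11-22: 17.5 × 84 = 1,470 mg
- Weeks 23-34: 10 × 84 = 840 mg
- Total over 238 days: 4,060 mg prednisone

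A 60 mg/day start with a linear fall to 25 mg/day changes the first line to 42.5 × 28 = 1,190 mg and the total to 4,550 mg.

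Appendix 4 equates methylprednisolone 4 mg with prednisone 5 mg, so a parenteral course of *x* mg methylprednisolone omits 1.25*x* mg. The documents give no value for *x*. If *x* were 250 mg, the omission would be 312.5 mg (312.5/4,060 = 7.7%). If it were 1,000 mg, it would be 1,250 mg (30.8%). These are assumptions that show how the formula behaves, not estimates.

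**The case against.** The strongest reply is that the protocol uses OCS loosely. Section 6.4 itself attaches the term to inhaled treatment, Section 5.5.2 uses it as shorthand for corticosteroids, Appendix 8 describes rescue in terms of the steroid dose, and the synopsis mentions prednisone alongside other immunosuppressive therapy. An assessor could reasonably score intravenous steroid as rescue. That stands as evidence of ambiguity. It does not supply a rule, and it means two assessors could score the same subject differently.

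The scenario is also narrow. Section 6.4 prefers an oral increase, with an IST change as the alternative, and a subject who has either is normally already counted. An admission would be reported as an SAE, so it is not lost to the primary safety endpoint. Efficacy detail is deferred to a SAP (Sections 8.5.1 and 8.8) that could settle the matter, but nothing in the combined document does so.

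A reader might infer several stronger points that the documents do not support:

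- *The sickest subjects are the likeliest to be misclassified.* Nothing in the documents says which subjects would receive parenteral steroid.
- *Eligibility has the same gap.* Exclusion 3 reads "Systemic (oral or parenteral) antibiotic or pulse OCS treatment for any indication within 42 days prior to randomization". Its opening words can govern the pulse steroid as well as the antibiotic, and an any-route reading of the entry criteria could change who enrols.
- *Later PET and LVEF values lose a rescue flag because of this gap.* The text gives no rule for those values after any rescue.
- *The omitted dose could rival the whole oral total.* That needs an assumed 3,000 mg methylprednisolone course (3,750 mg prednisone, 92.4%) set against the lowest oral schedule.

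**Conclusion.** The point holds in a limited form. Under the literal definition, parenteral corticosteroid given for worsening sarcoidosis with no other trigger met is neither a rescue event nor part of steroid use. A looser reading is possible, so the result depends on who scores it.

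The firm size is 10 percentage points per affected subject in a 10-subject arm or cohort. The number of such subjects is unknown and may be zero. The effect on steroid totals cannot be sized without a dose that the documents do not give. The 4,060 mg comparison rests on the assumed linear taper and a constant 10 mg/day after Week 22.

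The endpoints affected are secondary and descriptive, with no hypothesis testing (Section 8.5), and the primary safety endpoint does not depend on the rescue definition. The change is still worth making, because it is cheap and because the rescue definition also decides whether pre-rescue assessments are sought.

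**What to change.** For endpoint scoring and recording only:

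- In the Section 6.4 endpoint definition, count systemic corticosteroid by any route, given for sarcoidosis worsening, as a rescue event.
- Identify it from the concomitant-medication record and from the Appendix 1 row for steroid dose and rescue use, with footnote k extended to non-oral doses. Make sure route is recorded.
- Keep cumulative oral use as the named endpoint, and report total systemic steroid in prednisone equivalents (Appendix 4) beside it.
- State whether the same wording also triggers the Rescue Visit, the pre-rescue imaging and the Medical Monitor contact, so that scoring and conduct agree.
- Settle the rule before Cohort A is unblinded. Cohort B is open-label, so it should not wait for database lock.

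The inclusion and exclusion criteria stay as they are. The change prescribes no treatment, dose or clinical threshold. It costs a few lines of text and possibly one form field, since the drugs are already recorded. The small downside is that rescue rates and steroid totals may look slightly less favourable.
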